## 5.6 Duration of Follow Up and Active Disease Monitoring

### Disease Monitoring:

Participants who elect to discontinue treatment after having achieved MRD negative CR or CRi (or MRD- PR after C25) will be followed every 3 months (+/- 14 days) for active disease monitoring. Subjects are allowed to alternate visits with a local team so that they only need to be seen at the trial site every 6 months. They will be monitored until they resume treatment with venetoclax (if they show signs of progression by MRD positivity or clinical manifestations) or are removed from active disease monitoring for other reasons such as withdrawal of consent, removal from monitoring by treating investigator, lost to follow up, elect to go on to other CLL/RS directed therapy, or death.

### Assessments for Active Disease Monitoring:

- History and physical
- CBC differential and platelet count
- Serum Chemistry Panel including magnesium, uric acid, phosphorus and LDH
- CT or PET CT scan and response assessment as clinically indicated
  - De-identified scans must continue to be sent to the lead site to be centrally read for response
- Bone marrow biopsy and aspirate as clinically indicated and MRD sent for analysis
- MRD assessment in the peripheral blood every 3 months, or at minimum every 6 months

### Follow Up:

Those who are removed from treatment for reasons other than MRD negativity will be followed every 3 months for up to one year (+/- 14 days). During active follow up (not those who are in active disease monitoring) participants will be offered the opportunity to have follow up visits at their treating institution every 6 months (versus every 3) to minimize travel burden if they choose, so long as they are being clinically followed by a hematologist/oncology team locally every other visit, and relevant clinical information is being conveyed to the lead site for follow up data entry purposes.

CONFIDENTIAL

This document is confidential. Do not disclose or use except as authorized.

**Assessments for those who discontinue treatment for reasons other than MRD negative CR/Cri or PR after C25 :**

- History and physical
- CBC differential and platelet count
- Serum Chemistry Panel including magnesium, uric acid, phosphorus and LDH
- CT or PET CT scan and response assessment as clinically indicated
- Bone marrow biopsy and aspirate as clinically indicated

After the active disease monitoring and follow up periods are complete, survival follow up data will be collected indefinitely unless one of the following occurs:

- Death
- Lost to survival follow up
- Withdrawal of consent

Survival status may be collected by phone, email, or other traditional data collection methods indefinitely.

The reason for taking a participant off study, and the date the participant was removed, must be documented in the case report form (CRF).

## **5.7 Resuming Treatment after Discontinuation**

If a patient elects to discontinue therapy and is currently in active follow up, and the participant exhibits MRD positivity at least two times in the peripheral blood or exhibits clinical disease progression in the opinion of the investigator, the participant may resume venetoclax monotherapy.

If patients do not achieve MRD negativity or has evidence of disease progression after reaching full dose venetoclax monotherapy, they have the option to add duvelisib at the highest dose they previously tolerated and continue it until MRD negativity is achieved on two successive peripheral blood MRD assessments or indefinitely depending on tolerability.

A re-staging bone marrow evaluation (aspirate, core, FISH, cytogenetics, flow/MRD, pathology) and CT scan (or PET/CT if RS) is required prior to re-initiation of venetoclax. If there is no clinical evidence of disease and only MRD detectable disease, venetoclax can be resumed at 400 mg in the outpatient setting with TLS lab monitoring 6-8 hours and 24 hours after the initial dose. If there is clinical evidence of disease, ramp up per package insert of venetoclax to the dose the participant received during their last cycle on treatment is required. The participant will have the opportunity to increase their dose of venetoclax to the MTD if tolerated after discussion with the treating investigator. Study visit frequency will coincide with where the participant left off while they were on treatment. For example, if discontinuation occurred at the end of Cycle

CONFIDENTIAL

This document is confidential. Do not disclose or use except as authorized.

37, the participant would resume a q3 month assessment schedule after the appropriate ramp up cycle

### **5.8 Criteria for Taking a Participant Off Study (No longer being followed for Survival).**

Participants will be removed from study when any of the following criteria apply:

- Lost to follow-up
- Withdrawal of consent for data submission
- Death
- The study will no longer be collecting this data, and is considered complete

Participants may be followed for survival after completing the follow up portion of the study by phone, email, or other traditional data collection methods indefinitely.

The reason for taking a participant off study, and the date the participant was removed, must be documented in the case report form (CRF).

For Decentralized Subject Registrations, the research team updates the relevant Off Treatment/Off Study information in OnCore.

CONFIDENTIAL

This document is confidential. Do not disclose or use except as authorized.

## 6. DOSING DELAYS/DOSE MODIFICATIONS

Dose delays and modifications will be made as indicated in the following table(s). The descriptions and grading scales found in the revised NCI Common Terminology Criteria for Adverse Events (CTCAE) version 5.0 will be utilized for dose delays and dose modifications. A copy of the CTCAE version 5.0 can be downloaded from the CTEP website [http://ctep.cancer.gov/protocolDevelopment/electronic\\_applications/ctc.htm](http://ctep.cancer.gov/protocolDevelopment/electronic_applications/ctc.htm).

### 6.1 Duvelisib:

Participants will be monitored continuously for toxicity while on study therapy. Non-hematologic toxicity will be assessed using the NCI-CTCAE Version 5.0. Hematologic toxicity will be assessed by 2008 IW-CLL criteria (see [Appendix H](#)) for both CLL and RS patients.

If a patient has an adverse event of particular severity (see Table 3) **at least possibly related to duvelisib**, then dose modifications can be made according to Table 2. There should be no attempt to make up for doses omitted due to toxicity.

**Table 2: Dose levels of duvelisib**

Dose Level	Duvelisib Dose
-2	25 mg every other day
-1	25 mg daily
+1	25 mg BID

All duvelisib dose reductions should be discussed with the principal investigator. Duvelisib dosing may be withheld up to 28 days for toxicity.

If dosing is withheld for >28 days for toxicities that are related to duvelisib this will result in discontinuation of duvelisib treatment on the study. In these cases, patients can continue on venetoclax monotherapy.

In cases where duvelisib has been held >28 days, duvelisib may be resumed after discussion with the overall PI in cases where toxicity is thought to be due to a cause other than duvelisib. Any participant who requires > 2 dose reductions for the same toxicity will be discontinued from active treatment on the study.

Patients who have a dose reduction due to toxicity may be eligible for a dose increase back to the dose level prior to the reduction (i.e., the starting dose or dose of previous reduction if patient was dose reduced more than one level) if the following criteria are met:

1. Patient has tolerated the lower treatment dose for 2 or more treatment cycles
2. Patient has recovered to baseline levels from the toxicity which caused the dose reduction
3. Toxicity was not drug-induced colitis or pneumonitis

CONFIDENTIAL

This document is confidential. Do not disclose or use except as authorized.

**Table 3: Recommended Management/Next Dose for Duvelisib**

Event	Recommended Management/Next Dose for Duvelisib
≤ Grade 1 Hematologic or Non-Hematologic	Continue current dose
Grade 2 Hematologic or Non-Hematologic	Continue at current dose. If dose reduction considered, contact the principal investigator
Grade 3 Hematologic or Non-Hematologic (non-DLT)	Continue at current dose. If dose reduction considered, contact the principal investigator
Grade 3 Hematologic (DLT)	
First occurrence: Withhold and provide growth factor or transfusion support if indicated until return to grade 2 or baseline level; re-initiate therapy at current dose if duration ≤ 10 days. If duration >10 days, re-initiate therapy at one dose level lower.
 
Second occurrence: Withhold and provide growth factor or transfusion support if indicated until return to grade 2 or baseline level; re-initiate therapy at one dose level lower.
 
Third occurrence: Discontinue patient from study drug

Grade 3 Non-hematologic (DLT)	
First occurrence: Withhold until return to grade 1 or baseline level; re-initiate therapy at 25 mg daily.
 
Second occurrence: Withhold until return to grade 1 or baseline level; re-initiate therapy at 25 mg every other day.
 
Third occurrence: Discontinue patient from study drug
 
Exceptions: Patients with pneumonitis and skin reactions will discontinue active treatment on protocol

Grade 4 Non-hematologic (DLT) other than asymptomatic lab abnormalities	Discontinue patient from the study
Grade 4 Hematologic (DLT or non-DLT)	First occurrence: Withhold and provide growth factor or transfusion support if indicated until return to grade 2 or baseline level; re-initiate therapy at current dose if duration ≤ 10 days. If duration >10 days, re-initiate therapy at one dose level lower.

CONFIDENTIAL

This document is confidential. Do not disclose or use except as authorized.

Event	Recommended Management/Next Dose for Duvelisib
	Second occurrence: Withhold and provide growth factor or transfusion support if indicated until return to grade 2 or baseline level; re-initiate therapy at one dose level lower.
	Third occurrence: Discontinue patient from study drug

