### 5.3 Definition of Dose-Limiting Toxicity (DLT)

Dose-limiting toxicity (DLT) is based on the CTEP Active Version of the NCI Common Terminology Criteria for Adverse Events (CTCAE) Version 5.0. DLT refers to toxicities experienced at any time during the first cycle of study treatment, defined as the following:

- Grade 4 neutropenia lasting more than 5 days
- Febrile neutropenia of any duration ( $ANC < 1.0 \times 10^9/L$  and fever  $\geq 38.5^\circ F$ )
- Grade  $\geq 3$  thrombocytopenia with clinically significant bleeding
- Grade  $\geq 4$  infection by NCI-CTCAE criteria
- Any grade 3 or greater non-hematologic toxicity with the following exceptions:
  - Grade 3 or greater nausea/vomiting/diarrhea that persists for 7 days or less
  - Grade 3 asymptomatic laboratory abnormalities that improve to grade 2 or less within 3 days
- Any grade  $\geq 3$  diarrhea or vomiting or diarrhea that requires tube feeding, total parenteral nutrition, or requires or prolongs hospitalization
- Inability to receive Day 1 therapy of Cycle 2 after a delay in treatment of up to 21 days due to continued drug related toxicity from the prior cycle
- Severe cutaneous reaction (grade 3 or greater)
- Grade 4 elevation in ALT and/or AST or grade  $\geq 3$  elevation in ALT and/or AST occurring in the context of a Grade  $\geq 2$  elevation in bilirubin
- Grade 5 treatment-related adverse events

All toxicities will be considered relevant to determining DLTs and to reporting unless the event can clearly be determined to be unrelated to the study drug(s).

The DLT observation period is considered the period from the first dose of combination therapy through the completion of cycle 1. In the phase I study, if a patient comes off study due to a reason other than a DLT (e.g. disease progression) prior to the end of the DLT observation period, that patient can be replaced.

CONFIDENTIAL

This document is confidential. Do not disclose or use except as authorized.

Management and dose modifications associated with the above adverse events are outlined in Section 6.

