### 6.1.1 Management Guidelines for Hepatotoxicity:

For Grade 2 ALT/AST elevation (> 3 to 5 X ULN), maintain duvelisib dose and monitor at least weekly until return to < 3 X ULN. For Grade 3 ALT/AST elevation (> 5 to 20 X ULN), withhold duvelisib and monitor at least weekly until return to < 3 X ULN. Resume duvelisib at the same dose (first occurrence) or at a reduced dose for subsequent occurrences. For grade 4 ALT/AST elevation (> 20 X ULN), discontinue duvelisib.

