### 6.1.2 Management Guidelines for Diarrhea and Colitis:

Severe and/or serious diarrhea has been observed in subjects with hematologic malignancies receiving duvelisib. In some cases, diarrhea preceded a diagnosis of colitis. For patients presenting with mild or moderate diarrhea (Grade 1-2) (i.e., up to 6 stools per day over baseline) or asymptomatic (Grade 1) colitis, initiate supportive care with antidiarrheal agents, continue duvelisib at the current dose, and monitor the patient at least weekly until the event resolves. If the diarrhea is unresponsive to antidiarrheal therapy, withhold duvelisib and initiate supportive therapy with enteric acting steroids. Upon resolution of the diarrhea, consider restarting duvelisib at a reduced dose. For patients presenting with abdominal pain, stool with mucus or blood, change in bowel habits, peritoneal signs, or with severe diarrhea (Grade 3) (i.e., > 6 stools per day over baseline), withhold duvelisib and initiate supportive therapy with enteric acting steroids (e.g., budesonide) or systemic steroids. A diagnostic work-up to determine etiology, including colonoscopy when applicable, should be performed. Monitor at least weekly. Upon resolution of the diarrhea or colitis, restart duvelisib at a reduced dose. For recurrent Grade 3 diarrhea or recurrent colitis of any grade, discontinue duvelisib. Discontinue duvelisib for life-threatening diarrhea or colitis.

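### Table 3 fixes the duvelisib restart doses after a grade 3 non-hematologic DLT, so a patient already reduced to 25 mg daily restarts with no reduction (minor)

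*Combined protocol and SAP*

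**What the plan says.** Section 6.1, Table 2 sets three duvelisib levels: 25 mg BID, 25 mg daily and 25 mg every other day.

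Table 3 then uses two kinds of restart rule. In the hematologic rows the rule is relative: "re-initiate therapy at one dose level lower", applied at a first event lasting more than 10 days and at any second event. The reduction need not follow a DLT, because one of these rows is labelled "Grade 4 Hematologic (DLT or non-DLT". In the grade 3 non-hematologic DLT row the rule is absolute: "First occurrence: Withhold until return to grade 1 or baseline level; re-initiate therapy at 25 mg daily", and then "Second occurrence: Withhold until return to grade 1 or baseline level; re-initiate therapy at 25 mg every other day". A third occurrence stops the drug. Pneumonitis and skin reactions are excepted in the row and end active treatment.

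Four other places bear on this row:

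- Section 5.3 counts as a DLT "Any grade 3 or greater non-hematologic toxicity with the following exceptions", so the row covers a broad class of events.
- Section 6.1.2 says of severe diarrhea or colitis: "Upon resolution of the diarrhea or colitis, restart duvelisib at a reduced dose". Recurrent grade 3 diarrhea, or recurrent colitis of any grade, means stopping duvelisib.
- Section 6.1.1 says of grade 3 ALT/AST elevation: "Resume duvelisib at the same dose (first occurrence) or at a reduced dose for subsequent occurrences".
- The text under Table 2 allows an increase only under conditions, the first being "Patient has tolerated the lower treatment dose for 2 or more treatment cycles". The others are recovery to baseline and that the toxicity was not drug-induced colitis or pneumonitis.

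**The concern.** The fixed doses fit a patient who arrives at the row on the starting dose. They do not fit one who has already been reduced for blood counts. That patient has shown poorer tolerance, has now had a further DLT, and is directed back to the dose at which it occurred. Nothing in section 6.1 adjusts the cell for a previous reduction.

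For diarrhea or colitis the site holds two instructions, the same dose (Table 3) and a reduced dose (6.1.2), and no rule says which prevails. For grade 3 non-hematologic DLTs without text of their own, this row is the only specific guidance. Section 6.1 sends dose reductions to the principal investigator for discussion, but a restart at the same dose is not a reduction, so that check is not clearly triggered.

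What is at stake is the dose given to individual patients and consistency between sites, not the statistical design.

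**Working it through.** The plan gives no figure to reproduce here. The check traces Table 3 over the three levels of Table 2.

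**Inputs.** Average daily dose: 25 mg BID = 2 × 25 = 50 mg; 25 mg daily = 25 mg; 25 mg every other day = 25/2 = 12.5 mg.

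**First non-hematologic DLT.** Change = (restart dose − current dose)/current dose, with the restart fixed at 25 mg/day.

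| Dose at the event | Current mg/day | Restart in Table 3 | Change | Restart one level lower |
|---|---|---|---|---|
| 25 mg BID | 50 | 25 | (25 − 50)/50 = −50% | 25 (−50%) |
| 25 mg daily | 25 | 25 | (25 − 25)/25 = 0% | 12.5 (−50%) |
| 25 mg every other day | 12.5 | 25 | (25 − 12.5)/12.5 = +100% | none; stop |

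**Second non-hematologic DLT.** The restart is fixed at 12.5 mg/day. From 25 mg daily: (12.5 − 25)/25 = −50%. From 25 mg every other day: 0%.

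**Order of events.** Take one hematologic event longer than 10 days and one first non-hematologic DLT. Hematologic first: 50 to 25 (relative step), then 25 to 25 (fixed dose). Non-hematologic first: 50 to 25 (fixed dose), then 25 to 12.5 (relative step). The same two events leave the patient at 25 or 12.5 mg/day depending only on their order.

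**The every-other-day case.** Two tolerated cycles take at least 2 × 28 = 56 days. If DLT means cycle 1 only (5.3), cycle 1 lasts at most 49 days (5.1.1), and the combination part of it, from day 8, at most 49 − 7 = 42 days. Since 56 exceeds both, the increase conditions cannot be met in that window, and the higher dose in the cell would not be permitted.

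**Can the 25 mg daily case occur within cycle 1?** Assume a hematologic event that starts on day 8 and lasts 11 days, the shortest whole number of days above 10. With a 49-day cycle 1, 42 − 11 = 31 days remain. With a 20 mg start, cycle 1 is 7 + 5 × 7 = 42 days, leaving 35 − 11 = 24. If the accelerated Richter's ramp-up has a 28-day cycle 1 (assumed; its length is not stated), 21 − 11 = 10 remain. These figures rest on the day 8 start and are not maxima: a grade 4 hematologic event could begin in the first week, on duvelisib alone. They show only that the sequence fits.

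**The case against.** The case for leaving the table alone has real parts.

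- **It is guidance.** Table 3 gives recommended management, and physician discretion is kept (5.5). Nothing forbids a lower dose. This stands. A reader might infer that Table 3 obliges a site to double the dose of a patient on every-other-day dosing; the documents do not support that, because the table is advisory and the conditions for an increase still apply.
- **Dosing may be meant per toxicity.** Section 6.1 limits reductions for the same toxicity, and not every grade 3 event calls for a reduction: a grade 3 non-DLT event continues at the current dose. But the hematologic rows carry over any earlier reduction whatever its cause, so a per-toxicity intent does not explain the difference between rows. Venetoclax Table 5 also uses a relative step for grade 3 non-hematologic events, if indicated.
- **Much is covered elsewhere.** Diarrhea and colitis (6.1.2), ALT/AST (6.1.1), and pneumonitis and skin (the row's exception) have their own text. In section 7.4, the duvelisib-related events of grade 3 or higher in at least 5% of the extension-study patients were diarrhea, neutropenia, colitis and lipase increase; of the non-hematologic ones, only lipase (6.7%) has no text of its own. This limits the reach. It would be wrong to infer that the whole class of non-hematologic DLTs is without guidance.
- **Events would be noticed.** The earlier reduction should have been discussed with the principal investigator, and all adverse events are reported to the Overall PI (7.7). True, but noticing an event does not set the restart dose.
- **Less drug has a cost.** Section 8.1.1 gives a 7-hour half-life and a mean trough of 425 ng/mL at 25 mg BID, against a PI3K-delta IC90 of 361 ng/mL. Every-other-day dosing is a real trade-off, though it is the protocol's own lower level.

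**Conclusion.** The point holds as a minor defect in the dose-modification table. For a first grade 3 non-hematologic DLT, the fixed restart is a 50% cut from 25 mg BID, no cut from 25 mg daily, and a higher dose from 25 mg every other day. The 25 mg daily case is the realistic one, and for diarrhea or colitis it conflicts with section 6.1.2. The every-other-day case is rare.

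The conclusion assumes that the cell is read literally, and that an earlier hematologic reduction is still in force when the new event occurs. If DLT is confined to cycle 1, the route is narrow. If the row is also used in later cycles, it is wider; its provision for three occurrences, each with a hold and recovery, hints at this, but the protocol does not say so.

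Few patients are likely to be affected, and the documents do not allow the number to be estimated: the toxicity rates in section 7 are marginal and give no joint frequency. Because the row concerns DLTs, a reader might also infer that dose escalation or toxicity stopping is compromised. It is not: the row governs what happens after a DLT has been counted, and no endpoint, sample size or error rate depends on it.

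**What to change.** Reword the two cells of the grade 3 non-hematologic DLT row: *re-initiate at 25 mg daily (first) or 25 mg every other day (second), or one dose level below the dose at the time of the event (Table 2), whichever is lower; if already at 25 mg every other day, discontinue duvelisib.* Add to the row: *for ALT/AST follow 6.1.1 and for diarrhea/colitis follow 6.1.2 (including discontinuation for recurrent events) where these differ.*

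The added line is needed. Without it, the second-occurrence cell would still offer a restart where 6.1.2 says stop. The edit would also create a new disagreement with 6.1.1 for a first ALT/AST event at 25 mg daily, where the two texts now happen to agree.

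The cost is two cells and one line in an amendment. The reworded cells leave patients on 25 mg BID as they are. The added line changes what Table 3 gives them in two situations where the texts already disagree: a first ALT/AST event (same dose under 6.1.1) and recurrent grade 3 diarrhea or colitis (stop under 6.1.2). The clinical team should confirm both. A few already reduced patients would receive less duvelisib or stop it sooner; section 5 lets those who stop continue on venetoclax. The separate difference between Table 3 and 6.1.3 on skin reactions is left to the clinical team.

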### 6.1.1 Management Guidelines for Hepatotoxicity:

For Grade 2 ALT/AST elevation (> 3 to 5 X ULN), maintain duvelisib dose and monitor at least weekly until return to < 3 X ULN. For Grade 3 ALT/AST elevation (> 5 to 20 X ULN), withhold duvelisib and monitor at least weekly until return to < 3 X ULN. Resume duvelisib at the same dose (first occurrence) or at a reduced dose for subsequent occurrences. For grade 4 ALT/AST elevation (> 20 X ULN), discontinue duvelisib.

